9.8. Quality control

All data will be checked for completeness and outlying values by research group with requisite background and experiences in pharmacoepidemiology. We will archive all data files and data management and statistical programs for quality control.

9.9. Limitations of the research methods

Information bias

- Outcome misclassification is possible as the records of diagnoses reported in the HIRA database may be different from their actual diagnoses recorded in the hospital's electronic medical records.
- To minimize any bias arising from exposure misclassification, analyses will be repeated by using a 15 and 60-day grace period definition for non-overlapping successive prescriptions.

Selection bias

[figure not shown]
- By using the nationwide HIRA database that encompasses the entire Korean population of 50 million, this study is unlikely to miss out any patients with VTE in South Korea.

Confounding bias

- Owing to the nature of observational studies, residual confounding from unmeasured or unaccounted confounders may be present.
- Nevertheless, to minimize confounding bias, we will apply various PS approaches, with the IPTW approach applied as our main analysis.

External validity of study design

PFIZER CONFIDENTIAL

- Our study results will achieve generalizability by using the nationwide HIRA database.

Analysis limitations

- Potential incompleteness of information on potential confounders such as laboratory data are unavailable for assessment due to inherent limitations of the HIRA database as its primary purpose is for administrative means.
- Sensitivity analysis using the E-value will be conducted to quantify the impact of residual confounding from unmeasured or unaccounted confounders on the risk estimates for the association between apixaban use and risk of VTE recurrence and bleeding events.

Limitations due to missing and/or incomplete data

- HIRA data are released for research only after thorough internal review, this would not be applicable to HIRA data.

9.10. Other aspects

Not applicable.

10. PROTECTION OF HUMAN SUBJECTS

10.1. Patient information

This study involves data that exist in anonymized structured format and contain no patient personal information.

10.2. Patient consent

As this study involves anonymized structured data, which according to applicable legal requirements do not contain data subject to privacy laws, obtaining informed consent from patients by Pfizer is not required.

10.3. Institutional review board (IRB)/Independent ethics committee (IEC)

There must be prospective approval of the study protocol, protocol amendments, and other relevant documents (e.g., informed consent forms if applicable) from the relevant IRBs/IECs. All correspondence with the IRB/IEC must be retained. Copies of IRB/IEC approvals must be forwarded to Pfizer.

We will obtain a customized HIRA database between 1 Mar 2012 and 31 Dec 2019. This study was approved by the Sungkyunkwan University's Institutional Review Board (SKKU-IRB-2020-12-010), which waived the requirement for informed consent.

10.4. Ethical conduct of the study

The study will be conducted in accordance with legal and regulatory requirements, as well as with scientific purpose, value and rigor and follow generally accepted research practices described in Guidelines for Good Pharmacoepidemiology Practices (GPP) issued by the International Society for Pharmacoepidemiology (ISPE), Good Epidemiological Practice (GEP) guidelines issued by the International Epidemiological Association (IEA), Good Practices for Outcomes Research issued by the International Society for Pharmacoeconomics and Outcomes Research (ISPOR), International Ethical Guidelines for Epidemiological Research issued by the Council for International Organizations of Medical Sciences (CIOMS) and the European Medicines Agency (EMA) European Network of Centres for Pharmacoepidemiology and Pharmacovigilance (ENCePP) Guide on Methodological Standards in Pharmacoepidemiology.

11. MANAGEMENT AND REPORTING OF ADVERSE EVENTS/ADVERSE REACTIONS

This study involved data that exist as structured data by the time of study start.

In these data sources, individual patient data are not retrieved or validated, and it is not possible to link (e.g., identify a potential association between) a particular product and medical event for any individual. Thus, the minimum criteria for reporting an adverse event (AE) (e.g., identifiable patient, identifiable reporter, a suspect product, and event) cannot be met.

12. PLANS FOR DISSEMINATING AND COMMUNICATING STUDY RESULTS

In the event of any prohibition or restriction imposed (e.g., clinical hold) by an applicable competent authority in any area of the world, or if the investigator is aware of any new information which might influence the evaluation of the benefits and risks of a Pfizer product, Pfizer should be informed immediately.

Results of this study will be submitted for publication in an academic journal within one year after the end of the study. The target academic journals with their impact factors (as of 2019) are as below:

- European Heart Journal-Cardiovascular Pharmacotherapy (Impact Factor: 6.696)

PFIZER CONFIDENTIAL

- BMC Medicine (Impact Factor: 6.782)
- JAMA Network Open (Impact Factor: 5.032)
- Journal of Thrombosis and Haemostasis (Impact Factor: 4.157)
- Frontiers in Cardiovascular Medicine (Impact Factor: 3.915)

ANNEX 1. LIST OF STAND ALONE DOCUMENTS

None.

ANNEX 2. ADDITIONAL INFORMATION

Not applicable.

PFIZER CONFIDENTIAL

4. AMENDMENTS AND UPDATES

Amendment number	Date	Statistical Analysis Plan section(s) changed	Summary of amendment(s)	Reason
Amendment 1 (V.2.0)	27Apr2022	Study information	Changed index treatment grouping to PAC only, warfarin-based, and NOAC-based therapy.	Amendment following Protocol Administrative Change Letter in Oct 22, 2021
			Updated author information	Revised due to author's title change
		6. Research question and objectives	Added secondary objective of Phase I	Revised according to additional analysis in Phase I
		8.1 Study design	Updated Figure 1 and Figure 2	Amendment following Protocol Administrative Change Letter in Oct 22, 2021
		8.4 Variables	Revised the sentence regarding heparin bridging period	Amendment following Protocol Administrative Change Letter in Oct 22, 2021 (acute heparin therapy to be considered in all OACs)
			Added outcome definition for secondary objective of Phase I	Added according to additional analysis in Phase I
			Revised evaluation period of comorbidities (APS, history of cancer)	Amendment following Protocol Administrative Change Letter in Oct 22, 2021 and detailed explanation
		10. Statistical analysis	Added antiplatelet agents and azole antifungal agents	
			12. List of tables	Added data analysis for secondary objective of Phase I
			13. List of figures	Revised Tables 1, 2, 5, and 6, and added Tables 3, 4, 7, 8, 11, and 12

PFIZER CONFIDENTIAL

5. INTRODUCTION

Venous Thromboembolism (VTE), which includes deep vein thrombosis (DVT) and pulmonary embolism (PE), is a major cause of morbidity, mortality and healthcare expenditure. Although the occurrence of VTE in the Asian population has been lower than in Western populations, Its incidence has been reported to have increased rapidly in recent years.

For pharmacologic treatment of patients with VTE without cancer, the American College of Chest Physicians (CHEST) guidelines recommend the use of Non-Vitamin K antagonist oral anticoagulants (NOACs) over Vitamin K Antagonists (VKAs), with supporting evidences suggesting that each NOAC (e.g., apixaban) is effective at preventing recurrent VTE. In more recent treatment guidelines for the management of VTE released by the American Society of Hematology (ASH), NOACs are still recommended over VKAs for the initial management of VTE. NOACs are classified as new generation of anticoagulants with approved indications of the risk reduction of stroke and embolism in nonvalvular atrial fibrillation (NVAF) as well as prophylaxis and treatment of DVT and PE.

All NOACs became available as the first-line treatment of acute VTE in Korea after reimbursement expansion in May 2015. However, despite the increasing use of NOACs among VTE patients, there are still limited real-world evidence that assess treatment patterns as well as effectiveness and safety of the different anticoagulants especially among Asian population.

6. RESEARCH QUESTION AND OBJECTIVES

Research Question

What is the real-world evidence of anticoagulant treatment for patients with VTE that can be found in the nationwide claims database in Korea? The current study will take place in two phases:

Phase I involves a descriptive assessment of patient characteristics and treatment patterns in Korea as well as detailed power calculations for comparative study.

Phase II involves analyses of comparative safety between each NOAC and warfarin. These analyses will be implemented if there is sufficient power to enable scientifically valid inferences.

Primary Objectives of Phase I of the study

- To describe the sociodemographic and clinical characteristics of patients with VTE, overall and according to their index VTE treatment (parenteral anticoagulants [PAC] only, warfarin-based, NOAC-based)To describe index anticoagulant treatment patterns by investigating the utilization of different

anticoagulants, treatment interruption, switches, discontinuations, and overall treatment duration

Primary Objective of Phase II of the study

- To describe and compare the risk of clinical outcome (major bleeding) according to the specific type of OAC

[NOTE] Comparative analyses, especially NOAC vs NOAC direct comparisons, will be performed contingent on a feasibility assessment based on the descriptive analyses and the agreed opinion on scope after discussion with Eliquis Alliance Real World Data Review Committee.

Secondary objective of Phase I of the study

- To explore the relevant clinical events preceding treatment change from index anticoagulant

7. DATA SOURCES

We will use the nationwide HIRA database of South Korea between 1 Mar 2012 and 31 Dec 2019 to identify all variables (exposure, outcome, covariates) needed to conduct this study. The HIRA database includes healthcare utilization information of residents of South Korea, with patient identifiers anonymized. Information on age, sex, diagnosis (ICD-10 diagnostic code, date of diagnosis, setting of diagnosis [inpatient, outpatient, emergency department], and others), medications dispensed/prescribed (national drug chemical code based on the active ingredient, date of prescription, days' supply, dose, route of administration, and others). Previous validation study that compared diagnosis codes recorded in the HIRA to those of recorded in electronic medical records found an overall positive predictive value (PPV) of 82.3%.

[figure not shown]
7.1. Data management

Data management (data programming and analysis) will be conducted on secure servers with regular backup provided by HIRA.

8. RESEARCH METHODS

8.1. Study design

A retrospective, observational, nationwide population-based cohort study will be conducted to describe the treatment patterns of anticoagulation therapies prescribed to patients with VTE in South Korea, and assess the risk of major bleeding associated with apixaban and other NOACs use, as compared with warfarin, by using the Health Insurance Review and Assessment Service (HIRA) database from 1 Mar 2012 to 31 Dec 2019 (Figure 1).

Note: HIRA, Health Insurance and Review Assessment service; LMWH, low molecular weight heparin; NOAC, non-vitamin K antagonist; PAC, parenteral anticoagulants; VTE, venous thromboembolism; W, warfarin

[†]Record of active cancer is defined as first diagnosis of cancer with V code within the past 6 months of period prior to index date; or receiving anti-cancer treatment under cancer diagnosis with V code within the past 6-month period prior to index date.

[‡]Warfarin-based and NOAC-based include either PAC with warfarin/NOAC or warfarin/NOAC only

[figure not shown]
Figure 1. Study participants inclusion and exclusion criteria

8.2. Study population

The study cohort will be defined as patients diagnosed with VTE between 1 Mar 2013 and 30 Jun 2019. The cohort entry will be defined as the date of incident VTE diagnosis. The index date will be defined as the date of first prescription for anticoagulants within 30 days after the index VTE event. The length of the exclusion assessment window will vary depending on the condition, from 12-months at minimum to anytime prior to index date. The following patients will be excluded: A record of VTE diagnosis within the 12-month period prior to the index VTE encounter, diagnosed with atrial fibrillation, atrial flutter, mechanical heart valve replacement or mitral stenosis anytime prior to index date, had a record of Inferior Vena Cava filter anytime prior to index date, received anticoagulatory therapy within the 12-month period prior to index VTE encounter to restrict to new users of anticoagulatory therapy, prescribed two different anticoagulants on the same index date to prevent exposure misclassification, had a record of pregnancy within the 9-month period prior to index date, and for the Phase II of the study only, had a record of active cancer within six months period prior to index date.

Baseline sociodemographic characteristics (e.g., age, sex) will be assessed on the index date, whereas clinical characteristics (comorbidities, previous use of medications, Charlson comorbidity index [CCI], HAS-BLED scores, initial presentation of VTE, number of outpatient visits) will be assessed in the 6-month period prior to the index date except when otherwise specified in section 8.4 *Variables* (Figure 2).

Within this study cohort, we will describe the treatment patterns of anticoagulants prescribed for VTE treatment throughout the period of follow-up, defined as the period from the index date to the end of the study period. Moreover, if feasible, we will also examine the risk of major bleeding overall and by site, associated with each NOAC use, as compared with warfarin.

a. Baseline conditions included: Charlson comorbidity index, HAS-BLED scores, comorbidities (antiphospholipid syndrome, asthma, cancer, chronic obstructive pulmonary disease, chronic kidney disease, chronic liver disease, diabetes mellitus, fracture, heart failure, hyperlipidemia, hypertension, ischemic heart disease, myocardial infarction, stroke, trauma), previous use of medications (corticosteroids, nonsteroidal anti-inflammatory drugs, angiotensin-converting enzyme inhibitors, angiotensin II receptor blockers, antiplatelet agents, azole antifungal agents, β-blockers, calcium-channel blockers, selective serotonin reuptake inhibitors, proton pump inhibitors, diuretics, thiazides, vasodilators, estrogens, cyclooxygenase-2 inhibitors), initial presentation of VTE (DVT, PE, both DVT and PE), number of outpatient visits

b. Earliest of: outcome of interest (major bleeding event), treatment discontinuation, switch to another anticoagulant, in-hospital death, end of the study period (31 Dec 2019)

Note: Dx, diagnosis; NOAC, non-vitamin K antagonist oral anticoagulant; Rx, prescription; VTE, venous thromboembolism; PE, pulmonary embolism

Figure 2. Overall study schematic

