Cancer surgeries	Specified in 'cancer-related surgery' of section 8.3.2
Benign surgeries	R4123-R4129, R4421, R4430, R3975
Cancer-related event (active cancer)	C00-C97 (excluding non-melanoma skin cancer, C44) with V code (V011, V027, V193, V194)
Kidney function change	
Chronic kidney disease	N18, N19
Acute kidney injury	N17
Liver function change	
Liver disease	B15-B19, K70-K77
Abnormal liver function	R94.5, R74.0

- **Phase II of the study**

- Major bleeding will be defined using primary or secondary diagnosis codes according to the ICD-10 diagnostic codes shown in below table and classified by site (intracranial, gastrointestinal [GI], all others).

Major bleeding	ICD-10 diagnosis code	Diagnostic definition
Intracranial hemorrhage	I60, I61, I62, I690, I691, I692, S064, S065, S066, S068	Diagnosis code + admission code + brain CT or MRI code

		* Brain CT or MRI: CT: HA441, HA451, HA461, HA471, HA851 MRI: HE101, HE102, HE135, HE201, HE202, HE235, HE301, HE302, HE401, HE402, HE501, HE502, HE535
GI bleeding	I850, I983, K2211, K226, K228, K250, K252, K254, K256, K260, K262, K264, K266, K270, K272, K274, K276, K280, K282, K284, K286, K290, K3181, K5521, K625, K920, K921, K922	Diagnosis code + admission code
Other bleeding	D62, H448, H3572, H356, H313, H210, H113, H052, H470, H431, I312, N020-N029, N421, N831, N857, N920, N923, N930, N938, N939, M250, R233, R040, R041, R042, R048, R049, T792, T810, N950, R310, R311, R318, R58, T455, Y442, D683	Diagnosis code + admission code

- The earliest date of diagnosis of the major bleeding event after the index date will be defined as the outcome occurrence date.
- Patients will be followed up from the index date to the occurrence of an outcome, treatment discontinuation (30-day grace period), switch to another anticoagulants, in-hospital death, or end of the study period (31 Dec 2019) whichever comes first.

Potential Confounder(s)

- Sociodemographic characteristics such as age, sex, and index year will be assessed at the index date.
- CCI [2] and HAS-BLED [3] scores will be measured within the 6-month period prior to the index date.

List of CCI	Score	ICD-10 codes
Cerebrovascular disease	1	G45, G46, H34, I60-I69
Congestive heart failure	1	I09.9, I11.0, I13.0, I13.2, I25.5, I42.0, I42.5-I42.9, I43, I50, P29.0
Chronic pulmonary disease	1	I27.8, I27.9, J40-J47, J60-J67, J68.4, J70.1, J70.3

Dementia	1	F00–F03, F05.1, G30, G31.1

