9. STUDY SIZE

Phase I of the study (descriptive)

Not applicable as there are no specified *a priori* hypotheses

Phase II of the study (comparative)

- The estimated number of incident patients with VTE and no history of active cancer from the 2018 HIRA-National Patient Sample (HIRA-NPS) database is 1,465, where the HIRA-NPS database is a 3% random sample of the entire Korean population of 50 million. Based on this estimation, the projected number of patients with VTE from the entire Korean population (HIRA database) of 2018 is 48,828 (1,465 * 33.33).
 - Excluding period for patients with previous OAC treatment, VTE history or a history of active cancer was set to prior 3 months because HIRA NPS database used in sample size estimation was constituted of one-year data only.

1) Apixaban vs. warfarin

- Among the above-mentioned number of incident patients with VTE and no history of active cancer, those who newly initiated apixaban or warfarin was estimated to be 211 patients (14.4%; 211/1,465), where patients had no prescription for OACs and no history of VTE within the 3-month period prior to VTE diagnosis. From these 211 patients, there were 83 (39.3%) apixaban users and 128 (60.7%) warfarin users (based on 2018 HIRA-NPS data). Hence, the projected number of patients with VTE who newly initiated OACs to be present in the HIRA database in a single year is 7,032 patients (apixaban 2,766; warfarin 4,266). As this study aims to utilize data from 2013 to 2019 (7 years), the final projected number of patients with VTE who newly initiated apixaban or warfarin from the HIRA database is 49,224 patients (apixaban 19,362; warfarin 29,862).
- Considering a 95% for a two-sided CI level (α -error=0.05) and 80% power, the sample size for the comparative safety study for major bleeding events was calculated based on the following components:
 - HR for major bleeding events from previous literature: 0.31-0.75
 - Overall probability of major bleeding events from previous literature: 1.19%
 - Proportion of apixaban users among patients with VTE from the 2018 HIRA-NPS database: 39.3% (83 apixaban users; 128 warfarin users).

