 - 2,013 patients with VTE treated with apixaban or warfarin are required to detect at 5% α -error, and 80% statistical power, and HR of 0.31 by sample size calculations for survival analysis; alternatively (more conservative estimate), 33,340 patients with VTE treated with apixaban or warfarin are required to detect at 5% α -error, and 80% statistical power, and HR of 0.75 by sample size calculations for survival analysis.
 - As this study is expected to include 49,224 patients with VTE, with 19,362 patients treated with apixaban from the nationwide HIRA database, this study will have enough statistical power to test the hypothesis of the association between apixaban use and risk of bleeding events among patients with VTE.

2) Rivaroxaban vs. warfarin

- Among the above-mentioned number of incident patients with VTE and no history of active cancer, those who newly initiated rivaroxaban or warfarin was estimated to be 382 patients (26.1%; 382/1,465), where patients had no prescription for OACs and no history of VTE within the 3-month period prior to VTE diagnosis. From these 382 patients, there were 264 (69.1%) rivaroxaban users and 118 (30.9%) warfarin users (based on 2018 HIRA-NPS data). Hence, the projected number of patients with VTE who newly initiated OACs to be present in the HIRA database in a single year is 12,732 patients (rivaroxaban 8,799; warfarin 3,933). As this study aims to utilize data from 2013 to 2019 (7 years), the final projected number of patients with VTE who newly initiated rivaroxaban or

warfarin from the HIRA database is 89,124 patients (rivaroxaban 61,593; warfarin 27,531).

- Considering a 95% for a two-sided CI level (α -error=0.05) and 80% power, the sample size for the comparative safety study for major bleeding events was calculated based on the following components:
 - HR for major bleeding events from previous literature: 0.77-1.19
 - Overall probability of major bleeding events from previous literature: 8.1%
 - Proportion of rivaroxaban users among patients with VTE from the 2018 HIRA-NPS database: 69.1% (264 rivaroxaban users; 118 warfarin users).

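### Phase II sets no calendar-overlap rule, so the primary IPTW analysis is fragile for any NOAC rarely started before May 2015; separately, the study size counts 7 years for a 76-month window

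*SAP*

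**What the plan says.** The entry window in SAP 8.2 is common to every drug: "The study cohort will be defined as patients diagnosed with VTE between 1 Mar 2013 and 30 Jun 2019". The only extra Phase II restriction is on cancer: "and for the Phase II of the study only, had a record of active cancer within six months period prior to index date". SAP 5 dates the change in access: "All NOACs became available as the first-line treatment of acute VTE in Korea after reimbursement expansion in May 2015". The Protocol says the same in its abstract, and its sections 9.1 and 9.2 set the same window.

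Calendar time enters as a covariate (SAP 8.4): "Sociodemographic characteristics such as age, sex, and index year will be assessed at the index date". The primary analysis (SAP 10) uses weights of 1/PS and 1/(1-PS) and excludes the most extreme 1% of PS values. It does not say whether that percentile comes from the pooled or the arm-specific distribution. Balance is judged at an absolute standardized difference (SD) below 0.1, with no stated action if this fails. Trimming at 5% and 10%, PS deciles and SMR weights are sensitivity analyses.

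Phase II is gated (SAP 6): "These analyses will be implemented if there is sufficient power to enable scientifically valid inferences". A note adds that comparative analyses "will be performed contingent on a feasibility assessment based on the descriptive analyses". Neither names an overlap criterion. SAP 9 scales the 2018 sample up: "As this study aims to utilize data from 2013 to 2019 (7 years), the final projected number of patients".

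**The concern.** Weights can balance index year only if both drugs were started in every index year. If a NOAC had no starters in 2013-14, no NOAC patient can stand in for the warfarin starters of those years, and the arms keep different calendar mixes. If it had a handful, those few are weighted up to represent every starter in those years, and they then set the precision of the hazard ratio. Putting index year into the PS does not remove this difficulty; it is what produces the empty cell or the extreme weights.

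At stake is the primary estimate for each affected drug. Tables 13-16 would show a year imbalance but not a loss of effective sample size. The statement of enough statistical power also rests on a calendar span longer than the entry window.

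**Working it through.** Order throughout: apixaban/rivaroxaban/edoxaban/dabigatran.

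**Inputs.** From SAP 9: 2018 NOAC:warfarin counts 83:128, 264:118, 57:127, 26:129; scale factor 33.33; event probabilities 1.19/8.1/8.5/1.4%; conservative HRs 0.75/1.19/0.81/0.69. Window: 10+12+12+12+12+12+6 = 76 months; before May 2015: 10+12+4 = 26. Assumption: constant 2018 volumes, as in the plan's own projection. Early NOAC use is the unknown.

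**The plan's own figure.** Events = (1.96+0.84)²/[q(1-q)(ln HR)²], with q the NOAC proportion; N = events/event probability. Apixaban, q = 83/211, HR 0.75: 397.4 events, N = 33,397, against the plan's "33,340 patients with VTE treated with apixaban or warfarin are required". The other requirements reproduce within 0.4% (dabigatran at HR 0.69: 29,166 against 29,071).

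**No early use.** Warfarin starters of 2013-14 have PS near 0 and weight near 1. In units of one month of the 2018 sample counts, apixaban's weighted warfarin arm is 22×128 + 54×128 + 50×83 = 2,816 + 6,912 + 4,150 = 13,878. The 2013-14 share is 2,816/13,878 = 0.203, against 0 in the NOAC arm. SD = 0.203/√(0.203×0.797/2) = 0.71. For the four drugs: 0.71/0.52/0.76/0.83, before trimming.

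**Pooled 1% trim, zero use, apixaban.** The pair cohort is 13,878 × 33.33/12 = 38,546. A pooled 1% cut removes at most 385 patients. Even if all 385 came from the 7,821 warfarin starters of 2013-14, 7,436 of 38,161 remain: share 0.195, SD = 0.195/√(0.195×0.805/2) = 0.70. A cut at the NOAC arm's own 1st percentile would instead remove all 7,821, about 20% of the pair cohort.

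**Rare early use, 1% of the 2018 rate, apixaban.** PS in 2013-14 = 0.83/128.83, so the weight is 155. NOAC patients and weights by period, in the same units: 2013-14, 18.3 at 155.2; 2015, 667.3 at 3.30; 2016-19, 3,486 at 2.54. Effective size = (Σw)²/Σw² = 13,900²/469,700 = 411 units, or 1,142 patients of 11,587 (10%).

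| Early NOAC use | Result, four drugs |
|---|---|
| 1% of 2018 rate: NOAC patients in 2013-14 | 51/161/35/16 |
| 1% of 2018 rate: their weight | 155/46/224/497 |
| 1% of 2018 rate: effective NOAC size | 10/25/8/6% |
| 5% of the pair's early starters: effective NOAC size | 51/45/58/77% |
| 10% of the pair's early starters: effective NOAC size | 74/65/80/95% |

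**Restriction or full window.** Power = Φ(|ln HR|/√[(1/n_NOAC + 1/n_warf)/event probability] - 1.96), with effective sizes. At a 5% early share the full window gives 60/99.8/98/65%; May 2015 onward (50 months) gives 75/~100/99.5/67%. The two are equal at an early share of about 10/9/9/6%.

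**Study size.** 76/12 = 6.33 years, not 7. Apixaban: 211 × 33.33 × 76/12 = 44,540. For the four drugs: 44,540/80,636/38,841/32,719, against the stated 49,224/89,124/42,924/36,162. Apixaban at HR 0.75: 44,540 × 0.0119 = 530 events; Φ(√(530×0.2386)×0.2877 - 1.96) = 89.9% (92.5% on 7 years). Dabigatran at HR 0.69: 84.3% (87.7% on 7 years).

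**The case against.** The strongest objection is that the trigger is not in the documents. The May 2015 sentence says when all NOACs were first-line. A reader might infer that no NOAC was used before then and that the primary analysis fails for all four drugs. The text does not support that: some may have been in ordinary use earlier, and no yearly counts are given. The Protocol's background dates US approval of edoxaban to January 2015, which makes low early use of that drug plausible but says nothing about Korea. Figures 1 and 2 are not available, so a date rule drawn only there cannot be excluded. This stands, and it makes the point conditional.

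Partial safeguards also exist. Phase I includes detailed power calculations, index year by treatment and by individual NOAC (Tables 1 and 3), and OAC proportions by year and quarter. PS balance can be inspected before any outcome model is run. SMR weights avoid the empty cell, and an arm-specific trim would remove the imbalance when early use is nil. These reveal or bypass the problem. None tells the analyst what to do in the primary analysis, and the trim helps only on a reading the SAP does not state.

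Finally, the 7-year slip changes no conclusion about power on the plan's own assumptions. That is correct.

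**Conclusion.** The point holds as a conditional, drug-specific gap. It is serious when early use is nil or very rare, material for most of the drugs at an early share of 5%, and small above about 10%. Dabigatran is the least sensitive at a given share. All these sizes rest on constant 2018 volumes and on a PS driven by index year alone.

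The size of any bias in the hazard ratio cannot be derived, because the documents give no time trend in bleeding risk. A reader might also conclude that 1 May 2015 should be the start date for every drug; the documents do not support this, since it would discard usable overlap for any NOAC already established by then.

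The study-size error does not depend on early use. It overstates each projection by 84/76, about 10.5%. A reader might infer that the study is underpowered. It is not on the plan's assumptions: every corrected projection exceeds its highest stated requirement (44,540 against 33,340; 80,636 against 14,967; 38,841 against 9,703; 32,719 against 29,071).

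**What to change.** Before any Phase II outcome is analysed, fix a drug-specific index-date window for each primary comparison from the planned Phase I year and quarter counts. Open it at the first quarter from which the NOAC and warfarin each make up at least about 10% of that pair's starters, in that and every later quarter. A 5% threshold would lie below the break-even of about 6 to 10%. Then:

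- keep index year or quarter in the PS;
- state whether the 1%, 5% and 10% cut-offs are pooled or arm-specific;
- report weighted effective sample size per arm, and state the action if index-year SD reaches 0.1;
- keep the full window as a sensitivity analysis, and all patients in Phase I;
- restate projections and power on 76 months, and again on each final window.

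This takes a short paragraph in Protocol 9.2, 9.5 and 9.7 and in SAP 8.3, 9 and 10, with no new data. The cost is power where a window is short. At 50 months apixaban has about 29,300 patients (75% at HR 0.75) and dabigatran about 21,500 (67% at HR 0.69), below their requirements of 33,340 and 29,071, which could close the Phase II gate for them. Rivaroxaban (about 53,050) and edoxaban (about 25,550) stay above theirs. Where the early share is 10% or more in every early quarter, the rule keeps the early months and nothing is lost.
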